4.10. Merging Strata

If one of the strata includes subjects from only one of the two treatment arms in ITT population, the stratum cell will be combined with the closest neighbor stratum cell based on the subjects' baseline assessments within corresponding stratum for the corresponding population.

5. SUBJECT DATA

5.1. Subject Disposition and Study Populations

The number of subjects who entered and discontinued early (along with reasons for discontinuation) will be summarized during overall treatment period for ITT population, and during on-ataluren treatment period for as-treated-OL population. In addition, the number of subjects in as-treated-OL population will also be summarized.

5.2. Duration of Treatment with Study Drug

Duration of treatment with study drug during the overall treatment period will be calculated as:

$$\text{Duration (days)} = \text{Date of last dose of study drug} - \text{Date of first dose of study drug} + 1$$

Duration of treatment with study drug in weeks for the overall treatment period will be summarized continuously and categorically (<24 weeks, 24 weeks to <48 weeks, 48 to <72 weeks, 72 to <96 weeks, 96 to <120 weeks, 120 to <144 weeks, ≥144 weeks) based on ITT population.

Duration of treatment with ataluren during the on-ataluren treatment period will be calculated as:

$$\text{Duration (days)} = \text{Date of last dose of ataluren} - \text{Date of first dose of ataluren} + 1$$

Duration of treatment with ataluren in weeks for the on-ataluren treatment period will be summarized continuously and categorically (<24 weeks, 24 to <48 weeks, 48 to <72 weeks, 72 to <96 weeks, 96 weeks to <120 weeks, 120 to <144 weeks, ≥144 weeks) based on as-treated-OL population.

5.3. Study Drug Compliance

To evaluate study drug compliance, number of subjects with treatment interruption, and the duration of treatment interruptions will be summarized during overall treatment period for ITT population, and during on-ataluren treatment period for as-treated-OL population.

5.4. Demographic and Baseline Characteristics

Not applicable for open-label treatment period.

5.5. Disease Characteristics

Not applicable for open-label treatment period.

5.6. Medical History

Not applicable for open-label treatment period.

5.7. Concomitant Medications and Non-Drug Treatments for the On-Ataluren Treatment Period

Concomitant medications and non-drug treatments will be coded using the World Health Organization Drug Dictionary (WHODD), version September 2021 or higher.

Concomitant medications and non-drug treatments during the on-ataluren treatment period are defined as those taken any time from the first dose date of Ataluren through the last follow up date within study.

The use of concomitant medications and non-drug treatments will be summarized by Anatomical Therapeutic Chemical Level 3 and preferred term (PT) based on ITT, and as-treated-OL population. In addition, the use of corticosteroids and the changes in regimen of corticosteroids will be also summarized during overall treatment period for ITT population, and during on-ataluren treatment period for as-treated-OL population.

6. EFFICACY EVALUATION

The efficacy evaluations will be performed based on the overall treatment period using study baseline. By-visit summaries will be generated by treatment groups based on analysis visits.

6.1. Primary Analysis

Not applicable.

6.2. Secondary Efficacy Variables

6.2.1. Six-Minutes Walking Distance

The average rate of change from baseline in 6MWD over 144-weeks of treatment in the ITT population is considered the key secondary efficacy endpoint of interest for this study in open-label period. The ITT population was specified in the original SAP as a supportive population for the primary endpoint analysis given its importance in providing information on the broad study population (N=359) encompassing the full range of age and ambulatory function. The MMRM category model with a random intercept, baseline 6MWD as a covariate, and factors of baseline concomitant corticosteroid type (deflazacort, prednisone/prednisolone), baseline 6WMD category (<300 meters, 300 to <350 meters, 350 to <400 meters, ≥ 400 meters), baseline time to stand from supine (<5 seconds, ≥ 5 seconds), treatment, visit (analysis visit as a categorical variable), interaction of visit and treatment, interaction of visit and baseline 6MWD, and unstructured covariance matrix (UN), is considered the primary analysis model of interest. In case of non-convergence, other types of covariance matrix are to be used in the order of heterogenous Toeplitz, Toeplitz, and compound symmetric. For this analysis, any subject who lose ambulation during the study was assigned a 6MWD of 0 meters for the first visit in which the subjects lose ambulation and set to 0 meters for all subsequent visits while they participate in the study. The average rate of change in 6MWD over 144-weeks of treatment is calculated from the estimated change from baseline in 6MWD at Week 144 from the MMRM categorical model.

The example SAS code is listed below:

```
PROC MIXED data=<dataset> method=reml;

    CLASS Cortico TTSTBLC Subjid Trt C6WMD AVISIT;
    MODEL CHG6WMD = Cortico C6WMD TTSTBLC Trt B6WMD AVISIT AVISIT*B6WMD
                AVISIT*TRT/S CL;
    RANDOM Int / subject=Subjid;
    REPEATED AVISIT / type= un subject=subjid;
    LSMEANS TRT*AVISIT / pdiff CL;
RUN;
```

where

CHG6WMD = Change from baseline in 6WMD at each visit (Study baseline to Week 144)
B6WMD = Study baseline 6WMD
C6WMD = Study baseline 6WMD category
Cortico = Study baseline concomitant corticosteroid type
TTSTBLC = Time to stand from supine category
AVISIT = Analysis visits as categorical variable
Trt = Treatment group
Subjid = Subject
Int = Intercept

An ANCOVA model will also be used to evaluate the difference in change in 6MWD from baseline to Week 144 after missing data have been imputed via a pattern mixture model utilizing MI based on ITT population. The estimated treatment difference in change from baseline of 6MWD at Week 144 and the corresponding 95% CI will be provided. The ANCOVA model will include baseline concomitant corticosteroid type (deflazacort, prednisone/prednisolone), baseline 6MWD category (<300 meters, 300 to <350 meters, 350 to <400 meters, ≥400 meters), treatment, as well as baseline 6MWD as a covariate. The baseline time to stand from supine (<5 seconds, ≥5 seconds) will be included in the testing model in the ITT analysis. For this analysis, all 6MWD will be assigned to an analysis visit according to the analysis visit window described in Section 4.9. Any subjects who lose ambulation during the study will be assigned a 6MWT result of 0 meters for the visit in which the subjects lose ambulation and for all remaining visits while they participate in the study. For subjects with missing 6MWD due to other reasons, the missing assessments at post-baseline visits will be imputed using the pattern-mixture model MI assuming the missing values are missing not at random (MNAR) utilizing the complete case missing value pattern (CCMV - subjects who completed primary efficacy assessments without missing values). Detailed imputation method is described in [Appendix 2](#).

The example SAS code is listed below:

```
PROC MIXED data=<dataset> method=reml;  
  CLASS Cortico TTSTBLC Trt C6MWD;  
  MODEL CHG6MWD = Cortico TTSTBLC C6MWD Trt B6MWD /CL;  
  LSMEANS TRT / pdiff CL;  
RUN;
```

where

CHG6MWD = change from baseline in 6MWD at Week 144
B6MWD = Baseline 6MWD
C6MWD = Baseline 6MWD category
Cortico = Baseline concomitant corticosteroid type
TTSTBLC = Time to stand from supine category
Trt = Treatment group

The 6MWD values and the corresponding changes from study baseline values will be summarized by visit during overall treatment period based on ITT population. For these summaries, any subjects who lose ambulation during the study will be assigned a 6MWT result of 0 meters for the visit in which the subjects lose ambulation and for all remaining visits while they participate in the study.

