8 WITHDRAWAL OF SUBJECTS

All subjects who receive study drug should remain in the study whenever possible, including after loss of ambulation. However:

- The subject has the right to withdraw consent and discontinue study drug at any time.
- If the subject's condition substantially worsens after initiating study drug, the subject will be carefully evaluated by the investigator in consultation with the PTC Therapeutics medical monitor. The subject will be withdrawn from treatment if continuing would place them at risk.
- Upon consultation with the PTC Therapeutics medical monitor, the investigator may withdraw the subject from study drug, if, in the investigator's clinical judgment, it is not in the subject's best interest to continue.
- If the subject becomes significantly noncompliant with study drug administration, study procedures, or study requirements. In this event, the subject should be withdrawn from study treatment when the circumstances surrounding noncompliance increase risk to the subject or are anticipated to substantially compromise the interpretation of study results.
- The subject will be withdrawn from treatment if he is unable to tolerate study drug.
- The subject may be withdrawn from this study in circumstances where the blind is intentionally or accidentally broken.
- This study may be discontinued by the relevant regulatory authority and/or PTC Therapeutics at any time.

The date study drug is discontinued and the reason for discontinuation will be recorded in the source documents and in the eCRF.

When study drug is discontinued (regardless of the reason), the investigator should encourage that all of the evaluations required at the End of Treatment Visit be performed and that any additional evaluations be completed that may be necessary to ensure that the subject is free of untoward effects. The subject should be encouraged to seek appropriate follow-up for any continuing health problems.

Subjects may be replaced if they withdraw from the study because ataluren has become commercially available in their country. Subjects removed from the study for any other reason will not be replaced.

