4.8. Missing Data Handling

The analyses using a mixed model repeated measures (MMRM) model will be performed based on available data assuming the missing assessments are missing at random (MAR). As sensitivity analyses, missing assessments for the primary and key secondary endpoints based on the analysis of covariance (ANCOVA) will be imputed using pattern-mixture multiple imputation (MI) as described in Section 6.

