6.2.4. Loss of Ambulation and Stair Climb/Stair Descend

Time to loss of ambulation (LoA), defined as persistent inability to perform the 10-meter run/walk test within 30 seconds at any post-baseline visit and for all remaining visits, will be evaluated using Kaplan-Meier estimation, Log-rank test, and Cox proportional hazards model (assuming similar covariates as the primary efficacy model) during overall treatment period based on ITT population. Similar analyses will be performed for time to loss of 4-stairs climb and time to loss of 4-stairs descend, defined as persistent inability to perform the 4-stairs climb test or 4-stairs descend, respectively, within 30 seconds at any post-baseline visit and for all remaining visits.

A separate analysis will evaluate time to LoA during the overall treatment period in subjects with study baseline 6MWD <300 meters.

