APPENDIX 2. SAMPLE SAS PROGRAM FOR THE PRIMARY ANALYSIS FOR PRIMARY ENDPOINT USING ANCOVA MODEL

The analysis will employ of the following SAS procedures:

- For each analysis population or identified population for analysis, perform the MI for the population once. The MI results will be used for all analyses planned for the population.
- 100 datasets will be generated where missing data at intermediate visits will be imputed for each treatment group using non-missing data from all subjects within the treatment group by a Monte Carlo Markov Chain (MCMC) imputation model using the MCMC statement in the SAS PROC MI procedure. As a result, each dataset will only have missing ending data, or a monotone missing data pattern.
- For each dataset from the prior step, missing ending data will be imputed by a regression imputation model using the SAS PROC MI procedure with the REGRESSION option in the MONOTONE statement using the CCMV assuming that the missing values are MNAR. The regression imputation model includes an intercept and the slopes of the measurements from all previous visits for the imputation of subsequent visits.
- The resulting complete datasets from the prior step will be processed via a SAS DATA step to create change from baseline values for each treatment group at each visit.
- The resulting datasets will be analyzed using SAS PROC MIXED to perform the analysis of covariance for the primary efficacy endpoint by study visit.
- The SAS PROC MIANALYZE procedure will be used to combine the LS mean and treatment versus placebo difference estimates to produce the final analysis results.

Sample SAS code corresponding to the above steps appears below:

```
/******  
Multiple imputation assuming MNAR using complete case missing value pattern  
  
TRTn: Treatment (0=Placebo, 1=Ataluren)  
Cortico: Steriod use at randomization  
C6mwd: Baseline 6MWD categories  
Stand: Baseline stand from supine categories  
ITTfl: Identifier for ITT population  
*****/  
  
* 1st: Generate 100 datasets to impute missing interim data by treatment  
group using MCMC option;  
proc sort data=smwt; by trtn usubjid; run;  
proc MI data=smwt out=smwt_mono minimum=0 nimpute=100 minmaxiter=5000  
seed=93182;  
  WHERE ITTfl="Y";  
  BY trtn;  
  VAR SmwdWKBL SmwdWK12 SmwdWK24 SmwdWK36 SmwdWK48 SmwdWK60 SmwdWK72  
  SmwdWK96 SmwdWK120 SmwdWK144;  
  MCMC chain=multiple impute=monotone;
```

run;

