* 2nd: Impute missing ending data using monotone statement with regression option and assuming MNAR using CCMV;

```
proc sort data=smwt_mono out=smwt_mono; by _imputation_ trtn usubjid; run;
proc MI data=smwt_mono out=smwt_ccmv minimum=0 nimpute=1 minmaxiter=5000
seed=93035;
  WHERE ITTfl="Y";
  BY _imputation_ trtn;
  VAR SmwdWKBL SmwdWK12 SmwdWK24 SmwdWK36 SmwdWK48 SmwdWK60 SmwdWK72 SmwdWK96
SmwdWK120 SmwdWK144;
  MONOTONE reg(/details);
  MNAR Model (SmwdWK12 SmwdWK24 SmwdWK36 SmwdWK48 SmwdWK60 SmwdWK72 SmwdWK96
SmwdWK120 SmwdWK144/Modelobs=CCMV);
run;
```

* 3rd: Create datasets for ANCOVA;

```
data smwt_reg;
  set smwt_ccmv;
  AWeek= 0; Avalimp=SmwdWK0; CFBimp=SmwdWK0-BL6mwd; output;
  AWeek=12; Avalimp=SmwdWK12; CFBimp=SmwdWK12-BL6mwd; output;
  AWeek=24; Avalimp=SmwdWK24; CFBimp=SmwdWK24-BL6mwd; output;
  AWeek=36; Avalimp=SmwdWK36; CFBimp=SmwdWK36-BL6mwd; output;
  AWeek=48; Avalimp=SmwdWK48; CFBimp=SmwdWK48-BL6mwd; output;
  AWeek=60; Avalimp=SmwdWK60; CFBimp=SmwdWK60-BL6mwd; output;
  AWeek=72; Avalimp=SmwdWK72; CFBimp=SmwdWK72-BL6mwd; output;
  AWeek=96; Avalimp=SmwdWK96; CFBimp=SmwdWK96-BL6mwd; output;
  AWeek=120; Avalimp=SmwdWK120; CFBimp=SmwdWK120-BL6mwd; output;
  AWeek=144; Avalimp=SmwdWK144; CFBimp=SmwdWK144-BL6mwd; output;
```

run;

...

* 4th: Conduct ANCOVA analysis on imputed datasets;

```
proc sort data=adsmwdimp out=adsmwdimp; by _imputation_; run;
ods exclude all;
proc mixed data=adsmwdimp method=REML;
  WHERE ITTfl="Y" and Aweek=144;
  BY _imputation_;
  CLASS Cortico Trtn C6mwd Stand;
  MODEL CFBimp=BL6MWD Trtn Cortico Stand C6MWD / CL;
  LSMEANS Trtn/ diff=control('0') cl alpha=0.05;
  ods output diffs=diff_mi lsmeans=lsm_mi;
run;
ods exclude none;
```

* 5th: Use Proc MIAnalyze to obtain final analyiss results;

* LS Means;

```
proc mianalyze parms(classvar=full)=lsm_mi;
  CLASS Trtn;
  MODELEFFECTS Trtn;
  ods output parameterestimates=lsm_out;
run;
```

* Treatment differences;

```
proc mianalyze parms(classvar=full)=diff_mi;
  CLASS Trtn;
  MODELEFFECTS Trtn;
  ods output parameterestimates=diff_out;
run;
```

The table below lists the random seeds to be used for the primary and secondary analyses and some additional seeds should they be required. The random seeds were created using SAS uniform generator RAND(“Uniform”) with a seed of 20220316.

| Endpoint/Analysis | Seed for Step 1 (impute missing interim data) | seed for Step 2 (impute missing ending data) |
|--|---|--|
| 6MWD (mITT, Section 6.2.1) | 91137 | 7262 |

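### The 0 m score for lost ambulation ends when the boy leaves the study; his later 6MWD is then imputed as positive by the MI, and the MMRM can extrapolate it below zero

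*SAP*

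**What the plan says.** In the open-label SAP, Section 6.2.1, the lead analysis of 6MWD over 144 weeks is a categorical MMRM in the ITT population. A boy who loses ambulation receives 0 m at the first such visit, and later visits are "set to 0 meters for all subsequent visits while they participate in the study". The ANCOVA in the same section has the same limit: 0 m is given "for the visit in which the subjects lose ambulation and for all remaining visits while they participate in the study". The next rule there reads: "For subjects with missing 6MWD due to other reasons, the missing assessments at post-baseline visits will be imputed using the pattern-mixture model MI".

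Appendix 2 describes how this is done. Within each arm, "missing ending data will be imputed by a regression imputation model", fitted to complete cases, and the sample program bounds the draws: "proc MI data=smwt_mono out=smwt_ccmv minimum=0 nimpute=1 minmaxiter=5000". Section 4.8 says that the MMRM uses available data under missing at random, and that the ANCOVA after imputation is the sensitivity analysis.

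Section 6.2.4 defines loss of ambulation as "persistent inability to perform the 10-meter run/walk test within 30 seconds at any post-baseline visit and for all remaining visits". Protocol Section 8 adds: "All subjects who receive study drug should remain in the study whenever possible, including after loss of ambulation".

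The participation limit also governs Week 72, in double-blind SAP Section 6.1.3.1 and in Section 3.1.1 of the document on changes from the planned analysis.

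**The concern.** By the SAP's own definition, loss of ambulation lasts for all remaining visits, and its 6MWD score is zero. The outcome of a boy in that state is therefore settled by the scoring rule. The zero nevertheless stops when he leaves the study, and nothing states a score for the visits he would have had.

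The SAP treats the state as known elsewhere. In Section 6.2.3, an NSAA activity that cannot be done because of loss of ambulation scores 0 and is not missing. In Section 6.2.1.2, becoming non-ambulatory counts as 10% worsening.

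The worst outcome on the scale is thus handed to two models that treat it differently. If ataluren delays loss of ambulation, more placebo boys will be in this position, and the error will not cancel between arms. A gap between MMRM and ANCOVA could then be read as sensitivity to the missing-data assumption when the scoring rule caused it.

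**Working it through.** **What the plan gives.** It states no figure for this point. Two features of the plan fix the scale. The ITT population has 359 boys. The average rate of change is the MMRM change at the last visit divided by the number of weeks: in Table 1 of the changes document, 8.26 / 72 = 0.115 m/week (printed as 0.11) and 9.95 / 72 = 0.138 (printed as 0.14). A shift of x metres at Week 144 therefore moves the rate by x / 144 m/week.

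**Why the imputed value is positive.** The regression draws come from a continuous normal distribution and are restricted to 0 m or more, with no point mass at zero. For a predicted value of 0 m and residual SD s, the restricted draw has mean s × √(2/π) ≈ 0.80 s. It cannot average zero.

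**Why the MMRM can go below zero.** It imputes nothing, but the absent visits act through their conditional means given the observed visits, and no bound applies. If the earlier visits show decline, the conditional mean usually continues it.

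**Effect on the treatment difference, to a first approximation.** Let p be the share of an arm that leaves after loss of ambulation, and m the mean value that stands in for 0 m. Then

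shift (ataluren − placebo) ≈ p_A × m_A − p_P × m_P.

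If p_P > p_A, a negative m (MMRM) raises the difference and a positive m (MI) lowers it.

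**Simulation.** It used 359 boys, 1:1 allocation and nine post-baseline visits. The MMRM had unstructured covariance, visit-by-treatment, visit-by-baseline and 6MWD category; steroid type and time to stand were left out. The MI was within-arm complete-case regression restricted to 0 m or more, followed by ANCOVA. All rates are assumptions:
- mean decline of 0.6 to 1.3 m/week;
- loss of ambulation at a threshold of 50 to 150 m;
- leaving after loss of ambulation of 5%, 10% or 20% per 12 weeks, and otherwise 0.8%.

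A second set made loss of ambulation abrupt and unrelated to earlier 6MWD. There were 15 replicates per progressive scenario and 12 per abrupt one.

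Week 144 value standing in for the scored 0 m, among boys who left after losing ambulation:

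| | Progressive decline | Abrupt loss |
|---|---|---|
| MI, mean | 28 to 55 m | 60 to 115 m |
| MI, share above 0 m | 100% | 100% |
| MMRM-implied, mean | −96 to −173 m | −33 to +6 m |
| MMRM-implied, share of boys below 0 m | 94 to 99% | 39 to 87% |

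If m is equal in both arms, each percentage point by which p_P exceeds p_A shifts the difference by about 0.01 × 96 to 0.01 × 173 = 1.0 to 1.7 m upward (MMRM), or 0.01 × 28 to 0.01 × 55 = 0.3 to 0.6 m downward (MI), under progressive decline.

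Week 144 treatment difference in metres, with progressive decline of 0.9 m/week and a benefit of 0.3 m/week:

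| Leaving per 12 weeks | 5% | 10% | 20% |
|---|---|---|---|
| Boys leaving after loss of ambulation (of 359) | 25 | 42 | 68 |
| Complete data | 44.9 | 44.3 | 42.5 |
| MMRM as written | 46.9 | 49.3 | 52.2 |
| MMRM with 0 m carried forward | 45.1 | 46.3 | 42.1 |
| MI/ANCOVA as written | 43.4 | 43.5 | 40.8 |
| MI/ANCOVA with 0 m carried forward | 44.0 | 45.6 | 42.8 |

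As written minus carried forward:
- MMRM: 46.9 − 45.1 = +1.8; 49.3 − 46.3 = +3.0; 52.2 − 42.1 = +10.1 m.
- MI: 43.4 − 44.0 = −0.6; 43.5 − 45.6 = −2.1; 40.8 − 42.8 = −2.0 m.

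As a rate, the MMRM shift is 1.8 / 144 = 0.01 to 10.1 / 144 = 0.07 m/week. With no treatment effect, shifts were about 2 m or less in both analyses (largest 2.3 m).

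**Week 72.** A separate simulation (180 boys per arm, 6% with loss of ambulation by Week 72, 30% of those with a later visit leaving) gave arm-mean errors of +0.2 m (MI) and −0.6 m (MMRM). It was not repeated. Errors shared by both arms cancel in the difference.

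**The case against.** The strongest reply is that few boys may be affected. The protocol asks them to stay after losing ambulation and provides a premature-discontinuation visit (Section 6.2.1.4), and the double-blind sample size allows only about 5% discontinuation. The largest MMRM shift needs 68 of 359 boys (19%) to leave after losing ambulation. It also needs a benefit of 0.3 m/week, two to three times the 0.11 to 0.14 m/week reported for mITT at Week 72, although both arms take ataluren after that. The endpoint is secondary, with no multiplicity control. All of this stands and limits the size. None of it supplies a score.

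The MI as written also stayed within about 2 m of the complete-data result. At 10% leaving it was slightly closer than with zeros carried forward (43.5 against 45.6, complete data 44.3). So the MMRM is the larger problem.

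A reader might infer three stronger things that the documents do not support.
- *The MMRM always puts such a boy below zero.* The sign depends on the fitted covariance; with abrupt loss the implied mean was about zero in some scenarios. The protocol does describe progressive decline (Sections 11.2.3 and 11.2.4), which makes the negative value usual, but not certain.
- *The imputed distance is impossible.* Loss of ambulation means failing 10 m in 30 seconds. That pace held for six minutes gives 360 / 30 × 10 = 120 m, so a small positive distance is possible. Zero is a scoring convention.
- *An error in an arm mean can be set beside the 8.26 to 9.95 m treatment estimates.* Errors common to both arms cancel, and those estimates are mITT at Week 72, not ITT at Week 144.

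One could also argue that such a boy is not missing for other reasons. Then no rule covers him, and the sample program still imputes every missing ending value.

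**Conclusion.** The concern holds for Week 144. As written, the 0 m score ends at study exit. The MI then assigns a positive distance, and the unbounded MMRM can, and under progressive decline usually does, extrapolate below 0 m. The two can be pushed in opposite directions, so on this point the ANCOVA after MI is not a clean check on the MMRM.

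Under the assumed leaving rates and benefit, the Week 144 difference moved by about +2 to +10 m (MMRM) and −1 to −2 m (MI); without a benefit, by about 2 m or less. These figures include simulation noise and measure error against the SAP's own 0 m convention. The true size cannot be judged, because the documents do not say how many boys left after losing ambulation. At Week 72 the effect is very small.

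**What to change.** - In open-label SAP Section 6.2.1, delete the words that limit the score to participation, in both the MMRM and the ANCOVA text. Assign 0 m from the loss-of-ambulation visit through Week 144 whether or not the boy stays, before running PROC MI and the categorical MMRM. Section 3.5 of the changes document defers overall-period modelling to the final lock, so this belongs before that step.
- Report by arm how many boys left after losing ambulation.
- For Week 72 (double-blind SAP Section 6.1.3.1, changes document Section 3.1.1), run the same rule as a labelled sensitivity analysis.

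The cost is one phrase, one data step, one count table and one extra Week 72 run. The downside is that a boy who leaves after a single failed 10-meter test is scored 0 m although persistence was never observed. Report those boys separately.
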